4.4.2 Immunogenicity

4.4.2.1 Computed Values for Analysis

In order to appropriately manage extreme values (< lower limit of quantitation [LLOQ] and ≥ upper limit of quantitation [ULOQ]) for analysis purposes, the following computational rule is applied to the values provided in the clinical database for each blood sample (BL) drawn for analysis purposes:

- If a value is < LLOQ, then use the computed value LLOQ/2
- If a value is between ≥ LLOQ and < ULOQ, then use the value
- If a value is \geq ULOQ, then use the computed value ULOQ

4.4.2.2 hSBA Vaccine Seroprotection

The derived seroprotection indicator for hSBA will be "Yes" if hSBA titer is \geq 1:8, otherwise seroprotection will be "No". Note: If hSBA titer is missing, the seroprotection for hSBA will be missing.

4.4.2.3 Fold-rise

The derived endpoint of fold-rise is computed as follows for extreme values, to minimize the numerator and maximizes the denominator:

- If the baseline computed value is < LLOQ and the post-baseline computed value is < LLOQ, then the fold-rise is 1
- If the baseline computed value is \geq LLOQ and the post-baseline computed value is \geq LLOQ, then the fold-rise is post-baseline computed value / baseline computed value

- If the baseline computed value is \geq LLOQ and the post-baseline computed value is \leq LLOQ, then the fold-rise is (LLOQ/2) / baseline computed value
- If the baseline computed value is < LLOQ and the post-baseline computed value is ≥ LLOQ, then the fold-rise is post-baseline computed value /LLOQ

4.4.2.4 hSBA Vaccine Seroresponse

The derived seroresponse for serogroups A, C, Y, and W indicator for hSBA will be "Yes" if

- For a subject with a pre-vaccination titer < 1:8, the post-vaccination titer must be $\ge 1:16$.
- For a subject with a pre-vaccination titer $\geq 1:8$, the post-vaccination titer must be ≥ 4 -fold greater than the pre-vaccination titer.

4.4.2.5 rSBA Vaccine Seroresponse

The derived seroresponse for serogroups A, C, Y, and W indicator for rSBA will be "Yes" if

- For a subject with a pre-vaccination titer < 1:8, the post-vaccination titer must be $\ge 1:32$.
- For a subject with a pre-vaccination titer $\geq 1:8$, the post-vaccination titer must be ≥ 4 -fold greater than the pre-vaccination titer

4.4.3 Efficacy

Not applicable

4.4.4 Derived Other Variables

4.4.4.1 Age for Demographics

The age of a subject in the study was the calendar age in year at the time of inclusion.

4.4.4.2 Duration of a Subject in the Trial

The duration of a subject in the study is computed as follows:

Maximum (date of last visit, date of termination) – (date of V01 of that subject) +1.

4.4.4.3 **Duration of the Study**

The duration of study is computed in days as follows:

Maximum of all subjects (date of last visit, date of termination) – Minimum of all subjects (date of V01) + 1

5 Statistical Methods and Determination of Sample Size

The statistical analyses will be performed under the responsibility of the Sponsor's Biostatistics platform using SAS® Version 9.4 software or later. The results of the statistical analysis will be available in the final clinical study report (CSR).

For descriptive purposes, the following statistics in Table 5.1 will be presented. The confidence interval (CI) for the single proportion will be calculated using the exact binomial method (Clopper-Pearson method, quoted by Newcombe (1)). For immunogenicity results, assuming that Log₁₀ transformation of the titers / data follows a normal distribution, at first, the mean and the 95% CI will be calculated on Log₁₀ (titers / data) using the usual calculation for normal distribution (using Student's t distribution with n-1 degree of freedom), then antilog transformations will be applied to the results of calculations, in order to provide geometric means (GMs) and their 95% CI.

Table 5.1: Descriptive statistics produced

Baseline characteristics and follow-up description	Categorical data	Number of subjects.	
		Percentage of subjects.	
	Continuous data	Mean, standard deviation, quartiles, minimum, and maximum.	
Clinical safety results	Categorical data	Solicited: Number and percentage (95% CIs) of subjects.	
		Unsolicited: Number and percentage (95% CIs) of subjects, and number of events.	
Immunogenicity results	Categorical data (seroresponse, ≥ 4-fold rise, cutoff)	Number and percentage (95% CIs) of subjects.	
	Continuous data	Log10: Mean and standard deviation.	
	(titer / concentration)	Anti-Log10 (work on Log10 distribution, and anti-Log10 applied): Geometric mean, 95% CI of the geometric mean, quartiles, minimum, and maximum.	
		Graphical representation by Reverse Cumulative Distribution Curve (RCDC).	

5.1 Statistical Methods

5.1.1 Hypotheses and Statistical Methods for Primary Objective(s)

5.1.1.1 Hypotheses

Thirty days after the administration of MenACYW conjugate vaccine or Menactra[®], the percentages of subjects who achieve ≥ 1:8 in hSBA titers for meningococcal serogroups A, C, Y,

and W in the combined group (Group 5 + Group 7) are non-inferior to the corresponding percentages in the combined group (Group 6 + Group 8)

Null hypothesis (H0): $p(G5 + G7) - p(G6 + 8) \le -10\%$

Alternative hypothesis (H1): p(G5 + G7) - p(G6 + G8) > -10%

where p(G5 + G7) and p(G6 + G8) are the percentages of subjects who achieve $\geq 1:8$ in hSBA titers in the combined group (G5 + G7) and the combined groups (G6 + G8), respectively.

Each of the serogroups A, C, Y, and W will be tested separately. If the lower limit of the 2-sided 95% confidence interval (CI) of the difference between the 2 proportions is > -10%, the inferiority assumption will be rejected.

For the 4 non-inferiority hypotheses, the CI of the difference in proportions will be computed using the Wilson score method without continuity correction (2). The overall non-inferiority of this objective will be demonstrated if all 4 individual null hypotheses are rejected.

5.1.1.2 Statistical Methods

Each of the serogroups A, C, W, and Y will be tested separately. If the lower limit of the 2-sided 95% CI of the difference between the 2 proportions is > -10%, the inferiority assumption will be rejected. For the 4 non-inferiority hypotheses using the vaccine seroprotection rates, the 95% CI of the difference in proportions between (Group 5 + Group 7) and (Group 6 + Group 8) will be computed using the Wilson Score method without continuity correction (2).

Let $\hat{\theta} = p_1 - p_2$, then $L = \hat{\theta} - \delta$ and $U = \hat{\theta} + \varepsilon$ are respectively the lower and the upper limits of the CI, where:

$$\delta = Z_{0.025} \sqrt{\left\{ \frac{l_1(1-l_1)}{n_1} + \frac{u_2(1-u_2)}{n_2} \right\}}$$

$$\varepsilon = Z_{0.025} \sqrt{\left\{ \frac{l_2(1 - l_2)}{n_2} + \frac{u_1(1 - u_1)}{n_1} \right\}}$$

l₁ and u₁ are calculated from the CI of the single proportion in Group 1 given by:

$$\frac{(2n_1p_1 + Z_{0.025}^2 \pm Z_{0.025}\sqrt{(Z_{0.025}^2 + 4n_1p_1(1-p_1))})}{2(n_1 + Z_{0.025}^2)}$$

l₂ and u₂ are calculated from the CI of the single proportion in Group 2 given by:

$$\frac{(2n_2p_2 + Z_{0.025}^2 \pm Z_{0.025}\sqrt{(Z_{0.025}^2 + 4n_2p_2(1-p_2))})}{2(n_2 + Z_{0.025}^2)}$$

where $Z_{0.025}$ is the upper 97.5th percentile of the standard normal distribution.

The overall non-inferiority of this objective will be demonstrated if all 4 individual null hypotheses are rejected.

5.1.2 Hypotheses and Statistical Methods for Secondary Objective(s)

5.1.2.1 Hypotheses

No hypotheses will be tested. Descriptive statistics will be presented.

5.1.2.2 Statistical Methods

Immunogenicity

Secondary Objectives 1 and 2:

Descriptive statistics will be provided for the antibody titers against meningococcal serogroups contained in MenACYW conjugate vaccine and Menactra[®] in adults aged 18 to 55 years (Group 1 versus Group 2) or Quadri MeningoTM (or any locally available licensed meningococcal vaccine) in adults aged \geq 56 years (Group 3 versus Group 4) in India.

Secondary Objectives 3, 4, and 5:

Descriptive statistics will be provided for the antibody titers against meningococcal serogroups contained in MenACYW conjugate vaccine and Menactra[®] in adolescents and children aged 2 to 17 years in India and RSA combined ([Group 5 + Group 7] versus [Group 6 + Group 8]), India only (Group 5 versus Group 6), and RSA only (Group 7 versus Group 8).

In general, categorical variables in Cohorts Ia and Ib (in India), II (in India and RSA) will be summarized and presented by frequency counts, percentages, and CIs. The 95% CIs of point estimates will be calculated using the normal approximation for quantitative data and the exact binomial distribution (Clopper-Pearson method) (1) for percentages.

Descriptive analyses on A, C, Y, and W serogroups on D0 and D30 (+14 days) using hSBA and rSBA (in a subset)^b will be generated as follows:

Descriptive analyses of hSBA include but will not be limited to:

- Geometric mean titers (GMTs) and 95% CI
- Titer distribution and reverse cumulative distribution curves (RCDCs)
- Percentage of subjects with titer $\geq 1:4$ and $\geq 1:8$ and 95% CI

• Groups 5, 6, 7, and 8: 100 subjects each

·

Note: rSBA data will be generated in a subset of subjects as follows:

[•] Groups 1, 2, 3, and 4: 50 subjects each

- Percentage of subjects with titer ≥ 4-fold rise from pre-vaccination to post-vaccination, and 95% CI
- Percentage of subjects with hSBA vaccine seroresponse^c and 95% CI

Descriptive analyses of rSBA (in a subset) will include but not be limited to:

- GMTs and 95% CI in a subset of age groups
- Titer distribution and RCDCs
- Percentage of subjects with titer ≥ 1.8 and ≥ 1.128 and 95% CI
- Percentage of subjects with titer ≥ 4-fold rise from pre-vaccination to post-vaccination, and 95% CI
- Percentage of subjects with rSBA vaccine seroresponse^d and 95% CI in a subset of age groups

5.1.3 Statistical Methods for Observational Objective(s)

5.1.3.1 Hypothesis

No hypotheses will be tested. Descriptive statistics will be presented.

5.1.3.2 Statistical Methods

5.1.3.2.1 Immunogenicity

Descriptive statistics will be provided for the antibody titers against meningococcal serogroups contained in MenACYW conjugate vaccine and Menactra® in children and adolescents aged 2 to 17 years and another set of descriptive statistics on the same children and adolescents by age groups 2 to 9 years and 10 to 17 years in India and RSA combined and separated by each country as well.

In general, categorical variables for the full group in Cohort II and by age groups (2 to 9 years and 10 to 17 years) will be summarized and presented by frequency counts, percentages, and CIs in India and RSA combined ([Group 5 + Group 7]) versus [Group 6 + Group 8]), India only (Group 5 versus Group 6), and RSA only (Group 7 versus Group 8). The 95% CIs of point estimates will

• a post-vaccination rSBA titer ≥ 1:32 for subjects with pre-vaccination rSBA titer < 1:8, or

hSBA vaccine seroresponse for serogroups A, C, Y, and W is defined as:

[•] For a subject with a pre-vaccination titer < 1:8, the post-vaccination titer must be $\ge 1:16$;

[•] For a subject with a pre-vaccination titer ≥ 1:8, the post-vaccination titer must be at least 4-fold greater than the pre-vaccination titer.

d rSBA vaccine seroresponse for serogroups A, C, Y, and W is defined as:

a post-vaccination titer ≥ 4 times the pre-vaccination titer for subjects with pre-vaccination rSBA titer ≥ 1:8.

be calculated using the normal approximation for quantitative data and the exact binomial distribution (Clopper-Pearson method) (1) for percentages.

Descriptive analyses on A, C, Y, and W serogroups on D0 and D30 (+14 days) using hSBA and rSBA (in a subset) will be generated as follows:

Descriptive analyses of hSBA includes but will not be limited to:

- GMTs and 95% CI
- Titer distribution and RCDCs
- Percentage of subjects with titer $\geq 1:4$ and $\geq 1:8$ and 95% CI
- Percentage of subjects with titer ≥ 4-fold rise from pre-vaccination to post-vaccination, and 95% CI
- Percentage of subjects with hSBA vaccine seroresponse and 95% CI

Descriptive analyses of rSBA (in a subset) will be included but not be limited to:

- GMTs and 95% CI in a subset of age groups
- Titer distribution and RCDCs
- Percentage of subjects with titer $\geq 1:8$ and $\geq 1:128$ and 95% CI
- Percentage of subjects with titer ≥ 4-fold rise from pre-vaccination to post-vaccination, and 95% CI
- Percentage of subjects with rSBA vaccine seroresponse and 95% CI in a subset of age groups

5.1.3.2.2 Safety

The Safety Analysis Set (SafAS) is defined as those subjects who have received at least 1 dose of the study vaccine and have any safety data available. All subjects will have their safety analyzed according to the vaccine they actually received. Safety data recorded for a vaccine received out of the protocol design will be excluded from the analysis (and listed separately).

Safety analyses will include but not be limited to the following:

- The number and percentage of subjects reporting any solicited injection site reactions and solicited systemic reactions occurring from D0 to D07 after vaccination will be summarized by study group for intensity, time of onset period, days of occurrence, and action taken
- Immediate unsolicited systemic AEs within 30 minutes and unsolicited AEs occurring up to D30 after vaccination will be summarized
- The number and percentage of subjects reporting any unsolicited AEs will be summarized by study group, intensity, time of onset period, duration, and by MedDRA preferred term and system organ class (SOC), as well as by relationship to the study vaccine
- The number and percentage of subjects reporting at least one of any SAEs will be summarized by study group, seriousness criterion, outcome, and by MedDRA preferred term and SOC, as well as by relationship to the study vaccine

- The number and percentage of subjects reporting at least one of any AESIs will be summarized throughout the study
- Exact (Clopper-Pearson) (1) 2-sided 95% CIs will be calculated for the percentages

For exploratory purpose, main safety and immunogenicity parameters may be presented according to baseline HIV status in Groups 7 and 8.

5.1.4 Complementary Output

5.1.4.1 Subgroup Analysis

Subgroup analyses by gender, race (only if more than 5% of subjects had different race) and HIV status at baseline (only if more than 5% of subjects had different HIV status) for the RSA subjects will be provided in Appendix 15 of the CSR.

The gender subgroup analyses will have two categories (Female and Male), the race subgroup analyses will have four categories (White, Black or African American, Asian, and Other), and the HIV status at baseline subgroup analyses for the RSA subjects will have three categories (Positive, Negative and Unknown).

For primary and secondary immune endpoints after meningococcal vaccinations, subgroup analyses by gender, race will be conducted for all groups as well as groups combined by countries at D0 and 30 days after meningococcal vaccination. Subgroup analyses by HIV status at baseline will be conducted only for the RSA subjects at D0 and 30 days after meningococcal vaccination.

For safety responses, these subgroup analyses will be performed in all groups as well as groups combined by countries after meningococcal vaccination.

Immunogenicity analyses:

The subgroup analyses in immunogenicity will be performed based on PPAS.

- Percentage of subjects with hSBA antibody titers ≥ 1:8 against meningococcal serogroups A, C, Y, and W assessed at D30 (+14 days) after vaccination in adolescents and children aged 2 to 17 years in India and RSA ([Group 5 + Group 7] and [Group 6 + Group 8]) Per-Protocol Analysis Set
- hSBA GMTs and 95% CI Per-Protocol Analysis Set
- Percentage of subjects with hSBA titer≥ 1:8 and 95% CI Per-Protocol Analysis Set
- Vaccine seroresponse against meningococcal serogroups A, C, Y, and W measured by hSBA and 95% CI – Per-Protocol Analysis Set
- rSBA GMTs and 95% CI Per-Protocol Analysis Set
- Percentage of subjects with rSBA titer ≥ 1:128 and 95% CI Per-Protocol Analysis Set
- Vaccine seroresponse against meningococcal serogroups A, C, Y, and W measured by rSBA and 95% CI – Per-Protocol Analysis Set

Safety analyses:

Safety overview after vaccination – Safety Analysis Set

5.1.4.2 Sensitivity Analysis due to the COVID-19 pandemic

As this study was conducted during Coronavirus Disease 2019 (COVID-19) pandemic, the impact of COVID-19 pandemic situation on study conduct will be summarized through impact on visit procedures, study completion and major/critical protocol deviations due to COVID-19. The subset of subjects who were impacted by COVID-19 is defined as the subjects with at least one major/critical protocol deviation due to COVID-19 or who did not complete the study due to COVID-19. If more than 10% of subjects are impacted as per this definition, baseline and demographics characteristics, and the main immunogenicity and safety endpoints will also be summarized in the subsets of subjects impacted / non-impacted subjects to assess the potential impact of COVID-19 situation on study outcome. The outputs will be provided in Appendix 15 of the CSR.

The assessment of the impact of COVID-19 pandemic will be based on but not limited to the following analyses:

- To summarize the impact of COVID-19 on the overall study conduct
 - Early termination due to COVID-19
 - Impact on visit conduct (visit not done, partially done, data collection method/procedure change)
 - o Major and critical protocol deviations due to COVID-19
- To summarize disposition across study visits for subjects impacted by COVID-19
- To summarize baseline demographics for subjects impacted / non-impacted by COVID-19
- To provide an individual listing of subjects impacted by COVID-19 and how they were impacted
- To provide a listing of visits impacted by COVID-19 and how they were impacted
- To assess the potential impact of COVID-19 on the main immunogenicity and safety endpoints in the subsets of impacted / non-impacted subjects

Immunogenicity analyses

The sensitivity analyses in immunogenicity will be performed based on PPAS and FAS.

The primary endpoint for immunogenicity will be assessed:

 Percentage of subjects with hSBA antibody titers ≥ 1:8 against meningococcal serogroups A, C, Y, and W measured by hSBA assessed at D30 (+14 days) after vaccination in adolescents and children aged 2 to 17 years in India and RSA ([Group 5 + Group 7] and [Group 6 + Group 8])

Safety analyses

Safety overview after vaccine injection –Safety Analysis Set

5.1.4.3 Sensitivity Analysis due to Blood Sample Issues

If applicable and necessary, additional immunogenicity sensitivity analyses will be performed for subjects with blood samples handled incorrectly during collection, processing, storage or shipment, and may have potential impact on the analysis results (eg, blood samples stored out of temperature after a power outage) based on the PPAS. The outputs will be provided in Appendix 15 of the CSR.

The endpoint for the sensitive analyses will be the GMT.

• hSBA GMTs and 95% CI at each time point for each group by blood sample status – Per-Protocol Analysis Set

5.2 Analysis Sets

Three types of analysis sets will be used: the Full Analysis Set (FAS), the Per-Protocol Analysis Set (PPAS), and the Safety Analysis Set (SafAS).

5.2.1 Full Analysis Set

The FAS is defined as the subset of randomized subjects who received at least 1 dose of the study vaccine and had a valid post-vaccination blood sample result.

5.2.2 Safety Analysis Set

The SafAS is defined as those subjects who have received at least 1 dose of the study vaccine^e and have any safety data available.

All subjects will have their safety analyzed according to the vaccine they actually received.

Safety data recorded for a vaccine received out of the protocol design will be excluded from the analysis (and listed separately).

5.2.3 Per-Protocol Analysis Set

The PPAS is a subset of the FAS. The subjects presenting with at least one of the following relevant protocol deviations will be excluded from the PPAS:

- Subject did not meet all protocol-specified inclusion criteria or met at least one of the protocol-specified exclusion criteria
- Subject did not receive the vaccine
- Subject received a vaccine other than the one that he / she was randomized to receive
- Preparation and / or administration of the vaccine was not done as per-protocol
- Subject did not receive the vaccine in the proper time window

^e or which safety data are scheduled to be collected

- Subject did not provide the post-dose serology sample at Visit 2 in the proper time window or a post-dose serology sample was not drawn
- Subject received a protocol-prohibited therapy / medication / vaccine
- Subject had other protocol violations that affected the subject's immune response, as determined by the clinical team before locking the database.

In addition to the reasons listed above, subjects will also be excluded from the PPAS if their Visit 2 serology sample did not produce a valid test result (ie, results for all antigens are missing).

In the event of a local or national immunization program with oral poliovirus vaccine (OPV), subjects who receive 1 or more doses of OPV at any time during the study will not be withdrawn from the study. Every effort should be made to keep a gap of at least 2 weeks between OPV and MenACYW conjugate vaccines, if possible.

Other Analysis Set(s)

Enrolled / Screened subjects

As this study has no screening visit, enrolled subjects are subjects for whom signed off the inform consent form (ICF) and a CRF has been created.

Randomized subjects

A randomized subject is an enrolled subject for whom an injection group has been allocated and with any available data in CRF.

5.2.4 Populations Used in Analyses

All immunogenicity analyses will be performed on the PPAS analysis set and a supplemental analysis based on FAS will be performed to evaluate consistency of the results, If the difference between PPAS and FAS is greater than 10%. In the FAS, subjects will be analyzed by the vaccine group to which they were randomized.

The safety analysis will be performed on the SafAS. Subjects will be analyzed according to the vaccine they actually received.

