| 
Statistical Methods:
 | 
All immunogenicity analyses will be performed on the Per-Protocol Analysis Set (PPAS). Additional immunogenicity analyses will be performed for exploratory purposes on the Full Analysis Set (FAS) by randomization group. All safety analyses will be performed on the Safety Analysis Set (SafAS).
 
Primary Objective
 
Non-inferiority of MenACYW conjugate vaccine compared to Menactra[®] in terms of the percentages of subjects who achieve $\geq 1:8$ in hSBA titers in adolescents and children aged 2 to 17 years in India and RSA combined ([Gr 5 and Gr 7] versus [Gr 6 and Gr 8]).
 
Thirty days after the administration of MenACYW conjugate vaccine or Menactra[®], the percentages of subjects who achieve $\geq 1:8$ in hSBA titers for meningococcal serogroups A, C, Y, and W in the combined group (Gr 5 + Gr 7) are non-inferior to the corresponding percentages in the combined group (Gr 6 + Gr 8)
 
Null hypothesis (H0): $p(\text{G5} + \text{G7}) - p(\text{G6} + \text{G8}) \leq -10\%$ Alternative hypothesis (H1): $p(\text{G5} + \text{G7}) - p(\text{G6} + \text{G8}) > -10\%$
 
where $p(\text{G5} + \text{G7})$ and $p(\text{G6} + \text{G8})$ are the percentages of subjects who achieve $\geq 1:8$ in hSBA titers in the combined group (Gr5 + Gr7) and the combined groups (Gr6 + Gr8), respectively.
 |

| | |
|--|---|
| | 
Each of the serogroups A, C, Y, and W will be tested separately. If the lower limit of the 2-sided 95% confidence interval (CI) of the difference between the 2 proportions is $> -10\%$, the inferiority assumption will be rejected.
 
For the 4 non-inferiority hypotheses, the CI of the difference in proportions will be computed using the Wilson score method without continuity correction. The overall non-inferiority of this objective will be demonstrated if all 4 individual null hypotheses are rejected.
 |

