11.3 Data Review

A blind review of the data is anticipated through the data review process led by Data Management before database lock. The safety of the investigational product will be continuously monitored by the Sponsor. Periodic blinded safety data reviews will be performed by the Sponsor's SMT.

12 Statistical Methods and Determination of Sample Size

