12.2.4 Populations Used in Analyses

The primary immunogenicity analyses will be performed on the PPAS analysis set and will be confirmed on the FAS. In the FAS, subjects will be analyzed by the vaccine group to which they were randomized.

The safety analysis will be performed on the SafAS. Subjects will be analyzed according to the vaccine they actually received.

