5.7 Changes in the Conduct of the Trial or Planned Analyses

In protocol, the planned analysis the primary immunogenicity analyses will be performed on the PPAS analysis set and will be confirmed on the FAS. In SAP, we change that all immunogenicity analyses will be performed on the PPAS analysis set and a supplemental analysis based on FAS will be performed to evaluate consistency of the results, If the difference between PPAS and FAS is greater than 10%. In the FAS, subjects will be analyzed by the vaccine group to which they were randomized.

For safety analyses, will include the number and percentage of subjects reporting any unsolicited AEs will be summarized, not only non-serious AEs. Unsolicited AEs includes both serious (SAEs) and non-serious unsolicited AEs.

6 References List

- 1 Newcombe R.G., Two-sided confidence intervals for the single proportion: comparison of seven methods, Statistics in Medicine, (1998) 17, 857-872.
- Newcombe RG. Interval estimation for the difference between independent proportions: comparison of eleven methods. Stat Med. 1998; 17(8):873-90.

Signature Page for VV-CLIN-0646972 v1.0 MET55_SAP_CSR_CoreBody

Approve & eSign	
	Clinical

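### SAP 5.2.4 makes the FAS check of the primary non-inferiority result conditional on an undefined 10% difference; the protocol planned it unconditionally

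*SAP*

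**What the plan says.** The documents make three different statements about the FAS.

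- Protocol 12.2.4: "The primary immunogenicity analyses will be performed on the PPAS analysis set and will be confirmed on the FAS". No condition is attached.
- Protocol synopsis, Statistical Methods: "Additional immunogenicity analyses will be performed for exploratory purposes on the Full Analysis Set (FAS) by randomization group". The status is lower, but again there is no condition.
- SAP 5.2.4: all immunogenicity analyses use the PPAS, and "a supplemental analysis based on FAS will be performed to evaluate consistency of the results", subject to "If the difference between PPAS and FAS is greater than 10" (percent).

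SAP 5.7 acknowledges the departure. It restates the earlier plan ("In protocol, the planned analysis the primary immunogenicity analyses will be performed on the PPAS analysis set and will be confirmed on the FAS") and then repeats the new wording. It gives no reason and does not define the difference.

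The only other FAS analysis in the SAP is the COVID-19 sensitivity analysis in 5.1.4.2. It is reported by impacted and non-impacted subset and has its own gate: "If more than 10% of subjects are impacted as per this definition".

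The success rule in SAP 5.1.1.1 is "The overall non-inferiority of this objective will be demonstrated if all 4 individual null hypotheses are rejected". The FAS plays no part in it.

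**The concern.** The trigger is not specified well enough to program. The 10% could refer to the number of subjects, a seroprotection rate or the treatment difference. It could be a share of the FAS or of the PPAS, taken overall or by arm, cohort or serogroup. Two programmers could reach opposite decisions from the same data.

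The two main readings each have a problem. As a difference in results, the rule is circular, because the FAS must be analysed to learn whether it should be analysed. As a difference in set size, the rule can be applied without seeing results, but size alone does not show whether exclusions matter. That also depends on how the excluded subjects responded in each arm and on how close the result lies to the margin.

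At stake is whether a reader of the report can see how far the one confirmatory comparison depends on the per-protocol exclusions. One of these is an open-ended judgement by the clinical team about deviations affecting the immune response (SAP 5.2.3).

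**Working it through.** **Inputs from the documents.** Margin -10 points; lower limit of the two-sided 95% Wilson-score interval for a difference (SAP 5.1.1.2); 396 evaluable subjects per arm; serogroup A planned at 76% in both arms (SAP 5.5). Serogroup A has the lowest stated power.

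**The plan's own figure.** Farrington-Manning power at 396 per arm and one-sided 0.025 is A 90.8%, C 99.99%, Y 99.3%, W above 99.99%. The product is 90.1%, against the stated 90%, so the inputs reproduce.

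**When a set-size trigger stays closed.** As a share of the FAS, 10% is reached at 396/0.90 = 440 per arm, which is 44 exclusions; 45 are needed to exceed it. The planned 15% loss is 466 - 396 = 70 per arm. Subjects without a valid post-vaccination result are not in the FAS at all. So 45/70 = 64% of the planned loss would have to be deviations in subjects with a valid result before the FAS is analysed.

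**Break-even, set-size reading.** Assume 39 excluded per arm: 39/435 = 9.0% of the FAS, below the trigger. With L = (p1 - p2) - 1.96 × sqrt[l1(1 - l1)/n1 + u2(1 - u2)/n2], where l1 and u2 are single-sample Wilson limits:

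- PPAS 289/396 vs 301/396: difference -3.03 points, l1 = 0.6840, u2 = 0.7995, so L = -3.03 - 6.04 = -9.07%. Passes.
- Excluded responders 23/39 vs 30/39 (59% vs 77%, an 18-point gap) give FAS 312/435 vs 331/435: difference -4.37 points, l1 = 0.6732, u2 = 0.7986, so L = -4.37 - 5.80 = -10.17%. Fails.
- At 24/39 vs 30/39, L = -9.93%: still passes. At 20/39 vs 30/39, L = -10.88%.
- With equal PPAS rates (301 vs 301, L = -5.94%), a reversal needs 11/39 vs 30/39, a 49-point gap.

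**How often.** 2,000,000 simulated trials per row, independent binomials, 396 PPAS plus 39 excluded per arm. All rates other than 76% vs 76% in the PPAS are assumptions. MenACYW is listed first.

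| True PPAS rates | Rates among excluded | P(FAS fails given PPAS passes) |
|---|---|---|
| 76% vs 76% | 76% vs 76% | 0.9% |
| 76% vs 76% | 60% vs 60% | 1.5% |
| 73% vs 76% | 76% vs 76% | 2.6% |
| 73% vs 76% | 60% vs 60% | 4.1% |
| 73% vs 76% | 73% vs 76% | 4.5% |
| 73% vs 76% | 66% vs 76% | 11.7% |
| 73% vs 76% | 60% vs 76% | 20.8% |

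**Response-rate reading.** Within an arm, the PPAS rate minus the FAS rate equals the excluded fraction times (PPAS rate minus rate among excluded). At 76%, a 10-point shift needs an excluded fraction above 0.10/0.76 = 13.2% even if none of the excluded responded. A much smaller shift already matters: with an assumed 439 per arm in the FAS and control at 76%, a MenACYW rate 5 points lower gives a difference of -5.0 and a lower limit of -10.8%. That fails non-inferiority at half the trigger.

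**The case against.** The strongest reply has five parts.

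1. *The change is declared in SAP 5.7.* True, so this is not a hidden contradiction. Declaring it neither defines the trigger nor justifies dropping a protocol commitment.
2. *The two terms name sets, and the SAP's other triggers (5.1.4.1 and 5.1.4.2) count subjects, so set size is meant and the gate cannot be exploited after seeing results.* This is the better reading. It still leaves the denominator and the level open, and it still allows no FAS result for smaller exclusion counts.
3. *This FAS is not intention-to-treat.* It requires vaccination and a valid post-vaccination result, so it cannot test sensitivity to missing samples. That limits what the comparison can show, but it does cover the effect of the per-protocol exclusions.
4. *The risk is small.* The percentages in the table are conditional on a PPAS pass. At 73% vs 76% the PPAS passes about 62% of the time, so the joint chance of a PPAS pass and a FAS failure is about 1.6% to 2.8% without extra differences between arms, and about 7.3% and 12.9% in the last two rows. Without extra differences between arms, the opposite discordance, a FAS pass after a PPAS failure, is commoner: about 3% at 76% vs 76% and 7% to 9% at 73% vs 76%. All of this stands and limits the weight of the point.
5. *Blinding protects.* Protocol 6.4 keeps the sponsor blinded until database lock, and Protocol 11.3 states: "A blind review of the data is anticipated through the data review process led by Data Management before database lock". This makes arm-differential exclusion less likely, but it does not show a reader whether the two sets agree.

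**Conclusion.** The concern holds and should be fixed. The SAP replaces an unconditional check of the only confirmatory comparison with one that depends on an unexplained and undefined trigger. Sample size, power, alpha and the PPAS decision rule are unaffected.

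The exposure is confined to results near the margin. It is small (0.9% to 4.5% of PPAS passes in the scenarios run) unless excluded subjects respond worse on MenACYW than on Menactra, when it reaches 11.7% or 20.8%. Those last two figures rest on assumed gaps of 10 and 16 points among the excluded and on 39 exclusions per arm, and nothing in the documents predicts such gaps. Detecting them is the purpose of the FAS analysis, so making it conditional on set size alone weakens it.

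**What to change.** In SAP 5.2.4 and 5.7, remove the 10% condition for the primary endpoint. Report the four FAS differences with Wilson-score 95% intervals, by randomised group, beside the PPAS results in every case, as Protocol 12.2.4 provides. State that any disagreement will be discussed as a limit on robustness and is not a further success criterion. Align the synopsis wording with Protocol 12.2.4.

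If a trigger is kept for secondary or descriptive tables, define it as the percentage of FAS subjects excluded from the PPAS, and say whether it applies overall or by arm.

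The cost is a wording change and one extra table from data already collected. No subjects, visits or assays are added.
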